8.8.3 Retention of study documentation

Novo Nordisk will comply with all the requirements of Good Pharmacoepidemiological Practice (GPP) and relevant national legislation related to archiving of study documentation. Records containing patient sensitive data must not be archived by Novo Nordisk, but must be kept with physician and patient and according to local regulations pertaining to personal data protection.

The physician must agree to archive the documentation pertaining to the study in an archive after completion or discontinuation of the study, if not otherwise notified. The physician should not destroy any documents without prior permission from Novo Nordisk.

Novo Nordisk will retain the documentation pertaining to the study according to company procedure and in accordance with national regulations if they require a longer retention period.

8.9 Limitations of the research methods

As this is a non-interventional study, potential bias cannot be ruled out.

Data collection will reflect routine clinical practice rather than mandatory ass

Data collection will reflect routine clinical practice rather than mandatory assessments at prespecified time points, which may have an impact on the amount of data available and its interpretation.

Biases

Selection bias

 Protocol
 Date:
 23 November 2015
 Novo Nordisk

 Study ID: NN8022-4241
 Version:
 5.0

 UTN: U1111-1185-3661
 Status:
 Final

Page:

35 of 53

In order to minimize selection bias, the sampling strategy that was designed for the proposed study, will truly reflect real-life clinical practice since it will capture all possible treatment settings. In addition, selection bias due to sampling and participation will be addressed by comparing selected characteristics of the study patients and prescribers with those recorded in an external national database (IMSLifeLink).

Information bias

EU PAS No .:

At the prescriber (site) level, information bias is mitigated by the retrospective design. This study involves no intervention and treatment of patients considered eligible and their medical records at a site have been completed prior to the country-specific index date. Thus, the knowledge about this study (and its conduct) will not have had impact on the standard medical care and Saxenda® or Victoza® prescription practices at a site and will not have affected the treatment of patients. Data collected from medical records will therefore reflect real world medical practice.

At the patient level, misclassification of drug exposure has to be considered. Medical records provide detailed information on prescribed and/or dispensed medications but may not contain information on the intended duration of use (days of supply) and often do not contain information on the actual use of the medications by the patient. Thus, patients may be classified as exposed to a drug although they actually have not taken the drug. For this reason, great care will be taken to ensure the quality of the information that is abstracted, and prescribers' follow-up by clinical research associates (CRAs) will be enforced.

Missing Data

Some limitations with regard to data completeness may occur in this study, mainly related to the information captured in the patients' medical records. Measures to ensure the completion of the CRF is conducted in a systematic, professional, and unbiased manner include:

- CRF completion guidelines will provide consistent instructions on completion of the CRF.
- All individuals performing data abstraction from medical records will be trained on appropriate data abstraction techniques in order to minimize possible discrepancies between interpretation of the information recorded by the prescriber in the medical records and the individual performing the review and abstraction of the data.
- Missing data will be followed up on during remote monitoring contacts.

Protocol		Date:	23 November 2015	Novo Nordisk
Study ID: NN8022-4241		Version:	5.0	
UTN: U1111-1185-3661		Status:	Final	
EU PAS No.:	CONFIDENTIAL	Page:	36 of 53	

It is important to capture information on drug use from the start to end of treatment in order to fully assess drug utilisation. However, given the journey of patients with obesity or diabetes - these patients may be treated by several different specialist physicians - complete information over the 24 months of retrospective follow up may not be accessible by the site. For example, for patients whose treatment was initiated in settings other than the study site, there may be a lack of data on treatment initiation (e.g., brand name, start date, prescribed indication and target dose), which are required to fully evaluate drug utilisation. This is a potential limitation inherent of retrospective study designs. In this DUS, every effort will be made - as far as is possible - to obtain data from all relevant healthcare practices in order to capture the journey of patients as fully as possible.

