8.2.2 Inclusion criteria

To be eligible for the study, patients will be required to meet both of the following inclusion criteria:

1. Initiation of Saxenda® or Victoza® (initiation is defined as no prescription of the same brand within the previous 12 months).

Protocol		Date:	23 November 2015	Novo Nordisk
Study ID: NN8022-4241		Version:	5.0	
UTN: U1111-1185-3661		Status:	Final	
EU PAS No.:	CONFIDENTIAL	Page:	22 of 53	

2. Informed consent obtained before any study-related activities. Study-related activities (e.g. data collection) are any procedures that are carried out as part of the study, including activities to determine suitability of the study.

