8.3 Variables

Site characteristics:

To evaluate the representativeness of sites the following information will be collected for each participating site using a site questionnaire:

- Geographic location of physician site
- Specialty of participating physician (e.g., GPs, cardiologists, endocrinologists [or other diabetes and obesity specialists])
- Practice type (e.g., community hospital, academic/medical centre, office based)
- Practice size (number of physicians who practice at site)
- Patient volume (i.e., number of patients and estimated number of patients prescribed Saxenda[®] or Victoza[®]).

Additionally, the number of sites invited to participate within each specialty will be collected along with reason for refusal in order to evaluate the response rate and representativeness of the specialty. Sites and physicians will not be identifiable in the study report.

Patient demographics, medical history, and other characteristics:

- Date of birth
- Sex

Body weight (latest recording within 6 months before date of first prescription of Saxenda[®]), height, BMI (calculated), and date of anthropometric measurements (for Saxenda[®] patients only)

²⁾ Censoring at 24 months after launch

³⁾ Sex, age

 Protocol
 Date:
 23 November 2015
 Novo Nordisk

 Study ID: NN8022-4241
 Version:
 5.0

 UTN: U1111-1185-3661
 Status:
 Final

 EU PAS No.:
 CONFIDENTIAL
 Page:
 25 of 53

Drug utilisation:

Saxenda[®] or Victoza[®] patients:

- Brand name
- Indication prescribed at treatment initiation
- Target dose prescribed at treatment initiation
- Repeat prescription dates

Saxenda® patients only:

- Treatment start date and end date
- Comorbidities:
 - Dysglycaemia (T2DM or prediabetes), hypertension, dyslipidaemia, and/or obstructive sleep apnoea, before first prescription date. Diagnosis of dysglycaemia or dyslipidaemia may be based on relevant concomitant glucose lowering therapy (ATC code A10) or lipid lowering therapy (ATC code C10), respectively. In addition, diagnosis of dysglycaemia may be in the form of a relevant glycated haemoglobin (HbA1c), Oral Glucose Tolerance Test (OGTT) or fasting plasma glucose (FPG) measurement. According to the American Diabetes Association (ADA), prediabetes and diabetes may be defined based on the following laboratory cut-off values (4):

Prediabetes:

- FPG > 100 mg/dL (5.6 mmol/L) and < 125 mg/dL (6.9 mmol/L) and/or
- 2 hour post-challenge (OGTT) plasma glucose ≥ 140 mg/dL (7.8 mmol/L) and ≤ 199 mg/dL (11.0 mmol/L) and/or

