8.7.2 Statistical methods

Details of the data analyses, along with table, listing and figure (TLF) templates, will be fully described in a Statistical Analysis Plan (SAP).

In brief, the descriptive analyses will present Saxenda[®] and Victoza[®] utilisation by indication. Results will be evaluated by site characteristics, including country and geographic region within country, to ascertain any patterns of prescribing by specific indication. The main analysis will be to estimate the proportion of prescriptions outside label among Saxenda[®] or Victoza[®] patients during the entire study period in the countries of interest. The proportion of each of the forms of prescription outside label will be described (see section on prescription outside label). Characteristics of patients prescribed Saxenda[®] or Victoza[®] according to the respective approved SmPCs will also be evaluated.

Analyses on the following will be conducted:

Site characteristics

Descriptive statistics will be provided for the following variables:

- Geographic location of physician site (number and proportion)
- Specialty or area of primary practice (e.g. GPs, cardiologists, endocrinologists (or other diabetes and obesity specialists), etc.) (number and proportion)
- Practice type (e.g. community hospital, academic/medical centre, office based, etc.) (number and proportion)
- Number of physicians who practice at site (mean, standard deviation, median, first and third quartiles and range)
- Patient volume (i.e. number of patients and estimated number of patients using Victoza[®] or Saxenda[®]) (mean, standard deviation, median, first and third quartiles and range)

Patient demographics, medical history, and other characteristics:

Descriptive statistics will be provided for the following variables:

- Age (mean and standard deviation; number and proportion for age categories)
- Sex (number and proportion)

Protocol		Date:	23 November 2015	Novo Nordisk
Study ID: NN8022-4241		Version:	5.0	
UTN: U1111-1185-3661		Status:	Final	
EU PAS No.:	CONFIDENTIAL	Page:	30 of 53	

Drug utilisation:

Descriptive statistics will be provided for the following variables:

Saxenda® or Victoza® patients:

- Brand name (number and proportion)
- Indication prescribed at treatment initiation (number and proportion)
- Target dose prescribed at treatment initiation (number and proportion for target dose categories: 3.0 mg/day (for Saxenda® patients) and 1.2 mg/day, 1.8 mg/day or 3.0 mg/day (for Victoza® patients)

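### Patients started elsewhere may be counted under the enrolling site's specialty or practice type, because no variable records where the first prescription was written

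*Protocol*

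**What the plan says.** Four parts of the protocol bear on this point.

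- **Starts elsewhere are foreseen.** Section 8.9, under missing data, notes that "these patients may be treated by several different specialist physicians" and that "for patients whose treatment was initiated in settings other than the study site, there may be a lack of data on treatment initiation". It promises efforts "to obtain data from all relevant healthcare practices in order to capture the journey of patients as fully as possible".
- **Such patients are eligible and analysed.** In 8.2.2, "initiation is defined as no prescription of the same brand within the previous 12 months". The criterion concerns the brand and the preceding 12 months, not the place of the first prescription. Section 8.7.1 puts all recruited patients in the full analysis set.
- **Prescriber type comes from the enrolling site only.** In 8.3, "the following information will be collected for each participating site using a site questionnaire", and one of its items is "Specialty of participating physician". The patient-level items include "Indication prescribed at treatment initiation", but no item in 8.3, Table 1 or Table 2 says who wrote the first prescription or in what setting.
- **Patterns are sought by site.** Section 8.7.2 states: "Results will be evaluated by site characteristics, including country and geographic region within country, to ascertain any patterns of prescribing by specific indication". The list of site characteristics that follows in the same section includes specialty and practice type.

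**The concern.** BMI and comorbidity status before the first prescription, the prescribed indication and the target dose at initiation all describe the decision of whoever started treatment. If that was an endocrinologist and the patient is later enrolled at a general practice, the by-site tables count the start as general-practice prescribing. The reverse can also happen.

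Section 8.9 treats an outside start only as a source of missing data. Misattribution is a different problem. It appears when the start data are successfully recovered, so the better the retrieval effort works, the more outside starts enter the by-site tables under the enrolling site's label.

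At stake is a descriptive output that 8.7.2 asks for. Section 6 says that the usage patterns found could refine pharmacovigilance planning and risk management. Mixing the starts of two prescriber types pulls their observed proportions together and can hide which type starts patients outside label.

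**Working it through.** The protocol states no figure for this point, so there is none to reproduce. The check has two parts.

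**1. Can the data separate the two kinds of patient?**

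- Eligibility (8.2.2): an outside start does not exclude a patient.
- Analysis set (8.7.1): the patient is kept.
- Start data (8.9): these are sought from the other practice and, if found, entered for the patient at the enrolling site.
- Stratifier (8.3, 8.7.2): specialty and practice type come from the enrolling site's questionnaire.
- Link between the start and its setting (8.3, Tables 1 and 2): none.

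A recovered outside start is therefore tabulated under the enrolling site's type, and no collected variable would allow it to be flagged, set apart or reassigned.

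**2. How much could it matter?** All rates and mixing shares here are assumptions. Let p_A and p_B be the true outside-label proportions for starts by prescriber types A and B. Let f be the share of patients at type-A sites who were in fact started by type B.

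- One-way mixing: observed p_A = (1 − f)·p_A + f·p_B, so the observed gap is (1 − f)·(p_A − p_B).
- Mixing both ways at the same f: the observed gap is (1 − 2f)·(p_A − p_B).

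| f | Observed p_A, one-way (30% v 10%) | Gap, one-way (30% v 10%) | Gap, two-way (30% v 10%) | Gap, one-way (20% v 10%) | Gap, two-way (20% v 10%) |
|---|---|---|---|---|---|
| 0 | 30% | 20 points | 20 points | 10 points | 10 points |
| 10% | 28% | 18 | 16 | 9 | 8 |
| 20% | 26% | 16 | 12 | 8 | 6 |
| 30% | 24% | 14 | 8 | 7 | 4 |

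For example, at f = 20% with 30% v 10%, observed p_A = 0.8 × 0.30 + 0.2 × 0.10 = 0.26. The one-way gap is 0.26 − 0.10 = 0.16, and the two-way gap is (1 − 0.4) × 0.20 = 0.12.

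In patients: the full study plans 2 × 75 = 150 on Saxenda. If 10% to 30% of them were started in a setting of another type, that is 150 × 0.10 = 15 to 150 × 0.30 = 45 patients.

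The overall outside-label proportion does not move. Relabelling shifts a patient between rows of a table and leaves the total numerator and denominator as they were.

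**The case against.** The strongest case against runs as follows.

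- **The protocol speaks only of possibility.** Section 8.9 says such patients may occur and gives no share. Section 8.2 targets first-time patients through identified prescribers, so the share could be small. Misattribution also needs three things together: a start elsewhere, recovered start data, and an initiating setting of a different type. This stands, and it is why the point says may rather than are.
- **The sentence in 8.7.2 names only country and region.** These are less exposed, since an outside start will often lie in the same region. But the wording is inclusive, and specialty and practice type are on that section's own list.
- **Attribution to the treating site is a legitimate reading.** Section 8.7.2 looks at prescriptions over the entire study period, and a site that keeps renewing for weight management is itself prescribing for that indication. This is fair for renewals. It does not fit items recorded at initiation, which belong to the initiator.
- **Noise is larger than the shift.** With 75 patients on each side (an assumed even split of 150), the 95% half-width for 30% v 10% is 1.96 × √(0.21/75 + 0.09/75) ≈ 12 points. One-way mixing of 10% to 30% moves the gap by 2 to 6 points. This limits the importance of the point, but misattribution is systematic and costs little to avoid.
- **The analysis plan can handle it.** It can restrict or footnote tables, but not by a variable that the protocol's data list does not collect.

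A reader might also infer that the comparison with the IMS LifeLink prescriber distribution is distorted. The documents do not support that. The participating physician's specialty is recorded correctly wherever the patient was started, and the aim in 8.1.1 is a representative sample of prescriptions, not of first prescriptions only.

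**Conclusion.** The point holds with limited scope. The protocol foresees outside starts, keeps those patients, seeks their start data, and tabulates by the enrolling site's type without recording where treatment began. Start-based results may therefore be credited to the wrong specialty or practice type.

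The size is unknown. The illustrative shrinkage of a 20-point gap to between 18 and 14 points rests on assumed rates of 30% and 10% and on assumed one-way mixing of 10% to 30%. It also assumes that patients started elsewhere carry the initiating type's usual rate.

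A reader might infer that the main result is biased or that all outside-label categories are affected. Neither follows. The overall outside-label proportion, which is the main analysis in 8.7.2, is unchanged. Dose escalation, the stopping rule and concomitant GLP-1 receptor agonists arise after the start, under continuing care, and this mechanism does not touch them. No endpoint in 7.3 is defined by specialty. Where start data stay missing, the patient has a missing value, not a misattributed one. This is a cheap improvement to a secondary descriptive output.

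**What to change.** Add one item to 8.3 and to Tables 1 and 2: first prescription written at the enrolling site; at another setting (specialty and practice type if known); or unknown.

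In 8.7.2, state that the by-specialty and by-practice-type tables of start-based items (BMI and comorbidity status, indication, target dose at initiation) rest on patients started at the enrolling site, with all others in a separate row. Keep overall proportions on all patients.

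The cost is one case report form field and one sentence. The field will sometimes be unknown, because 8.9 accepts that information from other settings may not be accessible to the site, and the cells by specialty will be somewhat smaller. Adding the field before the pilot would also show how common outside starts are, since 8.1.1 already uses the pilot to assess the availability of variables. Adding it after abstraction would mean reopening charts.

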8.10 Other aspects

None

9 Protection of human subjects

To ensure the quality and integrity of research, this study will be conducted in accordance with the International Society for Pharmacoepidemiology guidelines for GPP (International Society for Pharmacoepidemiology [ISPE] 2007) (5) and in accordance with the European Network of Centres for Pharmacoepidemiology and Pharmacovigilance (ENCePP) Guide on Methodological Standards in Pharmacoepidemiology (ENCePP 2014) (6). The ENCePP Checklist for Study Protocols (ENCePP 2011), see Annex 2, will be completed, and the study will be registered in the ENCePP study registry (ENCePP 2010).

This PASS study will comply with the definition of the non-interventional (observational) study provided in Directive 2010/84/EU and the 2013 Guideline on (GVP: Module VIII – Post-Authorisation Safety Studies (EMA 2013) (7). The study will comply with the nature of non-interventional (observational) studies referred to in the International Conference on Harmonisation (ICH) harmonised tripartite guideline, Pharmacovigilance Planning - E2E (ICH 2004).

9.1 Informed consent form for study patients

Informed consent from all study participants is required.

In obtaining and documenting informed consent, the physician must comply with the applicable regulatory requirement(s) and adhere to the requirements in the Declaration of Helsinki (8).

Prior to any study-related activity, the physician must give the patient both oral and written information about the study in a form that the patient can read and understand. This includes the use of impartial witness where required.

A voluntary, signed and personally dated, informed consent form will be obtained from the patient prior to any study-related activity. Consent can be obtained both onsite during a visit or remotely. In

Protocol		Date:	23 November 2015	Novo Nordisk
Study ID: NN8022-4241		Version:	5.0	
UTN: U1111-1185-3661		Status:	Final	
EU PAS No.:	CONFIDENTIAL	Page:	37 of 53	

that latter, the physician will send two copies of the Informed Consent Form (ICF) to the patient's house who will sign both, keep one and send back the other in a pre-stamped envelope to the physician.

The task of seeking informed consent can only be performed by the physician or another medically qualified person delegated by the physician, if permitted by local regulation, who must sign and date the patient information/informed consent form. If information becomes available that may be relevant to the patient's willingness to continue participating in the study, the physician must inform the patient in a timely manner and a revised written informed consent must be obtained.

9.2 Data handling

If the patient withdraws the previously given informed consent, the patient's data will be handled as follows:

• Data collected will be used as part of the statistical analysis.

9.3 Institutional Review Boards (IRBs)/Independent Ethics Committee (IEC)

Before commencement of the study, the protocol, any amendments, patient information/informed consent form, any other written information to be provided to the patient, patient enrolment procedures, if any, the physician's current CV and/or other documentation evidencing qualifications and other documents as required by the local IRB/IEC should be submitted. The submission letter should clearly identify (by study identification number, including version, title and/or date of the document) which documents have been submitted to the IRB/IEC. Written approval/favourable opinion must be obtained from IRB/IEC before commencement of the study.

During the study, the physician must promptly in accordance with local requirements report the following to the IRB/IEC: amendments to the protocol according to local requirements, annually written summaries of the study status and other documents as required by the local IRB/IEC. Unexpected serious adverse reactions should be reported according to local regulatory requirements and will not be collected in this study.

Amendments must not be implemented before approval/favourable opinion, unless necessary to eliminate immediate hazards to the patients.

The physician must maintain an accurate and complete record of all submissions made to the IRB/IEC. The records should be filed in the physician's study file and copies must be sent to Novo Nordisk or CRO.

9.4 Regulatory authorities

Regulatory authorities will receive the non-interventional study application, amendments to the protocol and the non-interventional study report according to national requirements.

 Protocol
 Date:
 23 November 2015
 Novo Nordisk

 Study ID: NN8022-4241
 Version:
 5.0

 UTN: U1111-1185-3661
 Status:
 Final

 EU PAS No.:
 Page:
 38 of 53

